6.2.2. Study Period

Assessments and events will be classified according to the time of occurrence relative to the study intervention period.

Pre-Intervention is defined as time prior to the first dose of study intervention.

On-Intervention is defined as time from first dose to last dose date plus 14 days. If time of assessment or study intervention is not collected, the following assessment on the first dose date will be assumed to be taken prior to the first dose and therefore considered pre-intervention: ECG, Lab, and vital signs, and first dose date is considered on-intervention for AE and concomitant medication.

Post-Intervention is defined as any time post on-intervention window, i.e., > last dose date + 14 days.

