1.3.2. Single Ascending Dose (Treatment Periods 1 and 2)

Procedure	D-1	Treatment Periods 1 and 2										D2	D3
		Pre-dose	0h	5m	15m	30m	45m	1h	2h	4h	6h		
Site Visit	X							X					
Site Overnight Stay ¹	X							X					
Discharge from Site												X	
Phone Call													X
Review Inclusion and Exclusion Criteria	X												
Alcohol Urine Test	X												
Urine Drug Screen	X												
COVID-19 Testing ²	X												
Brief Physical Examination	X												
Inhaler Training (refresher) ³	X												
Randomisation (Period 1 only)		X											
Treatment Administration ⁴			X										
AE Review (include washout)				←								→	
SAE Review (include washout)			←									→	
Conmed Review			←									→	
Spirometry (FEV1)		X						X				X	
Vital Signs ⁵		X					X					X	X
12-Lead Safety ECG (single)		X						X				X	
Laboratory Safety Assessment ⁶	X											X	
Urinalysis	X												
Urine Pregnancy Test	X												
PK Blood Sample		X		X	X	X	X	X	X	X	X		
Genetic sample ⁷ (optional)		X											

1. Day -1 site admission would be optional.
2. To be performed according to local site policy on Day -1.
3. To be provided before first dose administration. If necessary, another inhaler refresher training may be provided in treatment period
4. Participants should fast for at least 6 hours before dosing until 1 hour post-dose. No water from 1 hour before dosing until 1 hour post-dose. See Section 5.3 for details.
5. Includes systolic and diastolic blood pressure, heart rate, respiration rate and tympanic temperature. Tympanic temperature will be measured once per day in the morning only.
6. Clinical chemistry and hematology only.
7. Genetic sampling can be conducted at any onsite visit during the study.

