4.1.2. Baseline Definition

Unless otherwise specified, baseline will be the last value/assessment before the first dose of study treatment (Day 1 pre-dose). If there are multiple assessments collected at the same scheduled time, the average of these assessments will be used as the baseline.

Unless otherwise stated, if baseline data is missing no derivation will be performed and baseline will be set to missing.

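### When a clock time is missing on the first dosing day, SAP 6.2.2 labels scheduled post-dose ECG and vital-sign readings as pre-dose, and the SAP does not rule out their use as baseline

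*SAP*

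**What the plan says.** SAP 6.2.2 sorts assessments into pre-, on- and post-intervention by when they occurred: "On-Intervention is defined as time from first dose to last dose date plus 14 days". It then gives a fallback. The trigger is "If time of assessment or study intervention is not collected", and the consequence is that "the following assessment on the first dose date will be assumed to be taken prior to the first dose and therefore considered pre-intervention". The data types follow: "ECG, Lab, and vital signs, and first dose date is considered on-intervention for AE and concomitant medication". No exception is made for a reading scheduled after dosing, and spirometry is not named.

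SAP 4.1.2 sets one baseline for the study: "baseline will be the last value/assessment before the first dose of study treatment (Day 1 pre-dose", the last words being a parenthetical gloss. Protocol 9.4.1 has the same definition. For QTcF, protocol 7.1.2 and 8.2.3 both say that baseline comes from the pre-dose ECGs taken before the first dose.

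In the protocol's schedule for Periods 1 and 2 (section 1.3.2), the row "12-Lead Safety ECG (single") is marked at pre-dose, at 1 hour and on Day 2. Vital signs are marked at pre-dose, once after dosing (the 45-minute column, as the table was extracted), and on Days 2 and 3. Safety laboratory tests are marked on Day -1 and Day 2 only.

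**The concern.** A default of this kind is harmless when the first dosing day holds only pre-dose readings. Here it does not. The rule overrides what the scheduled time point already shows and moves a post-dose reading to the wrong side of dosing. For AEs and concomitant medication the same section takes the opposite default and counts the first dose date as on-intervention, so the plan leans in different directions for different safety data.

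Two things are at stake. The first is the period label of the reading taken soon after the first exposure to the drug in this population. The second, which depends on how two SAP sections are read together, is whether that reading could be used as the baseline for later changes. One baseline serves all three periods, so such an error would not stay within Period 1.

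**Working it through.** No figure in the plan depends on this rule, so there is none to reproduce. The check sets the sections side by side and then sizes the consequence.

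**Which readings are exposed** (protocol 1.3.2, Period 1 Day 1; the rule concerns the first dose date only)

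| Data type | Scheduled that day | Post-dose readings exposed |
|---|---|---|
| ECG | pre-dose, 1 h | 1 |
| Vital signs | pre-dose, one post-dose set | 1 |
| Safety laboratory tests | none (Day -1 and Day 2) | 0 |
| Spirometry | not named in the rule | 0 |

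A missing assessment time affects only the reading concerned. A missing dosing time affects both the ECG and the vital-sign set, even when their own clock times are known.

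**Can an exposed reading become baseline?**

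1. SAP 6.2.2: the 1 h reading is assumed to precede the first dose.
2. SAP 4.1.2: baseline is the last value before the first dose.
3. Taken literally, when the dosing time is missing and the ECG times are known, the 1 h ECG is the last value deemed to precede dosing, so it is the baseline. The averaging clause in 4.1.2 does not apply, because pre-dose and 1 h are different scheduled times.
4. The gloss in 4.1.2 points to the scheduled pre-dose reading. If it governs, step 3 fails. The SAP does not say which section takes precedence.

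**Size, if step 3 holds.** Let s be the 1 h QTc minus the true pre-dose QTc, and d a later true increase from pre-dose.

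- Recorded change = d − s.
- At 1 h itself d = s, so the recorded change is 0.
- The SAP 6.2.1 flag needs a recorded change above 60 msec, that is d > 60 + s.

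The documents give no value for s, so a range is assumed (whole msec):

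| s (assumed) | Flag result |
|---|---|
| +10 | d of 61 to 70 missed |
| +20 | d of 61 to 80 missed |
| +30 | d of 61 to 90 missed |
| −10 | d of 51 to 60 flagged wrongly |

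The error can therefore go either way. One affected participant in a planned active group of 9 moves the group's mean change by s/9: 10/9 = 1.1, 20/9 = 2.2 and 30/9 = 3.3 msec.

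**Which outputs use baseline?** In SAP 6.2.1 only the QTc-increase flag does. The absolute QTc, PR, QRS and vital-sign limits do not. The spirometry flag compares 1 h with that day's pre-dose value. The other affected outputs are the change-from-baseline summaries, which SAP 4.2.2.2 places outside the primary endpoint.

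**The case against.** The strongest reply is that section 6.2.2 assigns study periods and never mentions baseline. Baseline has its own section, whose gloss names Day 1 pre-dose, and that section works with scheduled times when it averages repeats. With the protocol's QTcF wording added, a record labelled 1 h would not naturally be taken as baseline. This stands as a plausible reading and is why the baseline consequence must be stated conditionally. It does not settle the matter: the operative words in 4.1.2 refer to the last value before the first dose, 6.2.2 says which values are assumed to precede it, and no precedence is given.

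Second, a reader might infer that the post-dose value drops out of the safety results. The documents do not support that. SAP 4.2.2.2 summarises by visit, and SAP 4.2.1 runs the primary-endpoint window from randomisation to follow-up. Randomisation is scheduled at Period 1 pre-dose, so the value lies inside that window whatever its period label. The analysis that the SAP expressly ties to the on-intervention period is concomitant medication (SAP 6.1.4), which takes the opposite default. Display detail is left to the OPS, which is not among the documents reviewed.

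Third, the trigger should be rare. The first dose is given in the unit, and protocol 6.4 requires the date and time of clinic doses to be recorded in source. No rate of missing times is given. This stands, and it limits the severity.

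Fourth, 3 of the 12 participants receive placebo in Period 1, so their 1 h reading carries no drug effect. No hypothesis is tested. QTc withdrawal decisions use the protocol's own pre-dose baseline. All of this stands.

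**Conclusion.** The defect is real and minor. As written, the rule labels up to one scheduled post-dose ECG and one scheduled post-dose vital-sign set per affected participant as pre-intervention, although the schedule shows that they are not. That much follows from the text alone.

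The baseline consequence is possible but not established. It needs a missing clock time and a reading of the SAP in which 6.2.2 prevails over the gloss in 4.1.2. If both hold, that participant's later changes in the affected measure are shifted by the full 1 h difference, and the QTc-increase flag can be missed or falsely raised over a band as wide as that difference. The 10 to 30 msec used above are illustrations, not estimates.

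A reader might go further and conclude that a post-dose value will be subtracted from every later reading, or that one affected participant in nine means an 11% bias. The first assumes a precedence that the SAP does not state. The second is a headcount (1/9 = 11%), not a measure of bias. Scheduled laboratory tests, absolute-limit flags and the spirometry flag are untouched.

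**What to change.** Amend SAP 6.2.2 so that, when an assessment or dosing time is missing, ECG and vital-sign readings on the first dose date are classified by their nominal time point in the schedule of activities. Keep the pre-dose assumption only for readings without a scheduled post-dose label, such as unscheduled ones.

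State in SAP 4.1.2 that baseline is taken only from readings labelled pre-dose or earlier. This settles precedence and brings the SAP into line with protocol 7.1.2 and 8.2.3.

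The spirometry flag needs no change, since it already uses the daily pre-dose value.

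The cost is about one sentence in each of the two SAP sections and trivial programming. No new data are needed, because the nominal time points are already in the schedule.

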6.2.3. Study Day and Reference Dates

The safety reference date is the study intervention start date and will be used to calculate study day for safety measures.

The study day is calculated as below:

- Assessment Date = Missing → Study Day = Missing
- Assessment Date < Reference Date → Study Day = Assessment Date – Ref Date
- Assessment Date ≥ Reference Date → Study Day = Assessment Date – Ref Date + 1

6.2.4. Assessment Window

Refer to Section 5 (STUDY ASSESSMENTS AND PROCEDURES) in the Study Reference Manual (SRM).

6.2.5. Multiple measurements at One Analysis Time Point

When triplicate ECG assessments are taken, mean of the measurement will be calculated first and summary statistics will be based on the calculated mean. This will apply to both baseline and post baseline assessments.

For lab tests on a study day, if more than one assessment is taken on the same day, the test from a central lab will be taken over the test from a local lab. If multiple assessments are taken from the same type of lab, the worst case will be used.

6.2.6. Handling of Partial Dates

Element	Reporting Detail		
General	
 • Partial dates will be displayed as captured in participant listing displays. • However, where necessary, display macros may impute dates as temporary variables for sorting data in listings only. In addition, partial dates may be imputed for ‘slotting’ data to study phases or for specific analysis purposes as outlined below. • Imputed partial dates will not be used to derive study day, time to onset or duration (e.g., time to onset or duration of adverse events), or elapsed time variables (e.g., time since diagnosis). In addition, imputed dates are not used for deriving the last contact date in overall survival analysis dataset. 		
Adverse Events	
 • Partial dates for AE recorded in the CRF will be imputed using the following conventions: 
 
 Missing start day	If study intervention start date is missing (i.e. participant did not start study intervention), then set start date = 1st of month. Else if study intervention start date is not missing:	
 
 	Missing start day	If study intervention start date is missing (i.e. participant did not start study intervention), then set start date = 1st of month. Else if study intervention start date is not missing:
Missing start day	If study intervention start date is missing (i.e. participant did not start study intervention), then set start date = 1st of month. Else if study intervention start date is not missing:		

CONFIDENTIAL

Element	Reporting Detail	
		
 • If month and year of start date = month and year of study intervention start date, then 
 – If stop date contains a full date and stop date is earlier than study intervention start date, then set start date= 1st of month. – Else set start date = study intervention start date. 
Else set start date = 1st of month.

	Missing start day and month	
If study intervention start date is missing (i.e. participant did not start study intervention), then set start date = January 1.
 
Else if study intervention start date is not missing:
 
 • If year of start date = year of study intervention start date, then 
 – If stop date contains a full date and stop date is earlier than study intervention start date, then set start date = January 1. – Else set start date = study intervention start date. 
Else set start date = January 1.

	Missing end day	A '28/29/30/31' will be used for the day (dependent on the month and year).
	Missing end day and month	No Imputation
	Completely missing start/end date	No imputation
Concomitant Medications/ Medical History	Missing start day	
 • Partial dates for any concomitant medications recorded in the CRF will be imputed using the following convention: 
 • If study intervention start date is missing (i.e. participant did not start study intervention), then set start date = 1st of month. 
Else if study intervention start date is not missing:
 
 • If month and year of start date = month and year of study intervention start date, then 
 – If stop date contains a full date and stop date is earlier than study intervention start date, then set start date= 1st of month.

CONFIDENTIAL

Element	Reporting Detail	
		
 – Else set start date = study intervention start date. 
Else set start date = 1st of month.

	Missing start day and month	
If study intervention start date is missing (i.e., participant did not start study intervention), then set start date = January 1.
 
Else if study intervention start date is not missing:
 
 • If year of start date = year of study intervention start date, then 
 – If stop date contains a full date and stop date is earlier than study intervention start date, then set start date = January 1. – Else set start date = study. intervention start date. 
Else set start date = January 1.

	Missing end day	A '28/29/30/31' will be used for the day (dependent on the month and year).
	Missing end day and month	A '31' will be used for the day and 'Dec' will be used for the month.
	Completely missing start/end date	No imputation

6.2.7. Abbreviations

Abbreviation	Description
AE	Adverse Event
BL	Baseline
CI	Confidence Interval
CPMS	Clinical Pharmacology Modelling & Simulation
CS	Clinical Statistics
CSR	Clinical Study Report
%CV	Percent Coefficient of Variation
DP	Decimal Places
eCRF	Electronic Case Record Form
IA	Interim Analysis
MMRM	Mixed Model Repeated Measures
OPS	Output and Programming Specification
PCI	Potential Clinical Importance
PK	Pharmacokinetic
PT	Preferred Term
PopPK	Population PK
QC	Quality Control
QTcF	Frederica's QT Interval Corrected for Heart Rate
SAP	Statistical Analysis Plan

CONFIDENTIAL

Abbreviation	Description
SOC	System Organ Class

6.2.8. Trademarks

Trademarks of the GlaxoSmithKline Group of Companies
NONE

Trademarks not owned by the GlaxoSmithKline Group of Companies
WinNonlin

